Now think about all the different kinds of pain your child may have. Compared to before your child started taking the medicine for this study, would you say your child's overall pain is:

Please tick (ü) one box only:

- c Much Better
- c Moderately Better
- c A Little Better
- c About the Same
- c A Little Worse
- c Moderately Worse
- c Much Worse

Think about your child's tumour-related problems other than pain (such as moving, vision, hearing, appearance, etc.). Compared to before your child started taking the medicine for this study, would you say your child's tumour-related problems are:

Please tick (ü) one box only:

- c Much Better
- c Moderately Better
- c A Little Better
- c About the Same
- c A Little Worse
- c Moderately Worse
- c Much Worse

Appendix J Changes Related to Mitigation of Study Disruptions Due to Cases of Civil Crisis, Natural Disaster, or Public Health Crisis

Note: Changes below should be implemented only during study disruptions due to any of or a combination of civil crisis, natural disaster, or public health crisis (eg, during quarantines and resulting site closures, regional travel restrictions and considerations if site personnel or study participants become infected with SARS-CoV-2 or similar pandemic infection) during which participants may not wish to or may be unable to visit the study site for study visits. These changes should only be implemented if allowable by local/regional guidelines and following notification from the Sponsor and instructions on how to perform these procedures will be provided at the time of implementation.

Please note that during civil crisis, natural disaster, or public health crisis, some study assessments and procedures may not be conducted due to international or local policies or guidelines, hospital or clinic restrictions and other measures implemented to ensure the patient's safety. If in doubt, please contact the AZ Study Physician.

J 1 Reconsent of Study Participants During Study Interruptions

During study interruptions, it may not be possible for the participants to complete study visits and assessments on site and alternative means for carrying out the visits and assessments may be necessary, eg, remote visits. Reconsent should be obtained for the alternative means of carrying out visits and assessments and should be obtained prior to performing the procedures described in Section . Local and regional regulations and/or guidelines regarding reconsent of study participants should be checked and followed. Reconsent may be verbal if allowed by local and regional guidelines (note, in the case of verbal reconsent the ICF should be signed at the participant's next contact with the study site). Visiting the study sites for the sole purpose of obtaining reconsent should be avoided.

J 2 Rescreening of Participants To Reconfirm Study Eligibility

Additional rescreening for screen failure due to study disruption can be performed in previously screened participants. The investigator should confirm this with the designated study physician.

In addition, during study disruption there may be a delay between confirming eligibility of a participant and either enrolment into the study or commencing of dosing with IP. If this delay is outside the screening window specified in Section 1.1, the participant will need to be rescreened to reconfirm eligibility before commencing study procedures. This will provide another opportunity to re-screen a participant in addition to that detailed in Section 5.4. The

procedures detailed in Section 1.1, 5.1 and 5.2 must be undertaken to confirm eligibility using the same randomization number as for the participant.

J 3 Home or Remote Visit to Replace On-site Visit (where applicable)

A qualified HCP from the study site or TPV service will visit the participants home / or other remote location as per local standard operating procedures (SOPs), as applicable. Supplies will be provided for a safe and efficient visit. The qualified HCP will be expected to collect information per the clinical study protocol (CSP). [If applicable, assessments will be performed according to a revised Schedule of Assessments (SoA)].

J 4 Telemedicine Visit to Replace On-site Visit (where applicable)

In this appendix, the term telemedicine visit refers to remote contact with the participants using telecommunications technology including phone calls, virtual or video visits, and mobile health devices.

During a civil crisis, natural disaster, or public health crisis, on-site visits may be replaced by a telemedicine visit if allowed by local/regional guidelines. Having a telemedicine contact with the participants will allow adverse events, concomitant medication, and other relevant data to be reported and documented.

J 5 At-home or Remote Location IP Administration Instructions (where applicable)

If a site visit is not possible, at-home or remote location administration of IP may be performed by a qualified HCP, provided this is acceptable within local regulation/guidance, or by the patient or his/her caregiver. The option of at-home or remote location IP administration ensures participants safety in cases of a pandemic where participants may be at increased risk by traveling to the site/clinic. This will also minimize interruption of IP administration during other study disruptions, eg, site closures due to natural disaster.

J 5.1 At-home or Remote Location IP Administration by a Qualified HCP or TPV Service (where applicable)

A qualified HCP from the study site or TPV service should administer the IP at the participant's home or other remote location according to the CSP. All necessary supplies and instructions for administration and documentation of IP administration will be provided. Additional information related to the visit can be obtained via a telemedicine or home visit.

J 5.2 At-home or Remote Location IP Administration by the Participants or His/Her Caregiver (where applicable)

Prior to at-home or remote location IP administration the investigator must assess the participant or his/her caregiver to determine whether they are appropriate for at-home or remote location administration of IP. Once the participant or his/her caregiver is deemed appropriate for at-home or remote location administration, he/she must receive appropriate training. All necessary supplies and instructions for administration and documentation of IP administration will be provided. More information related to the visit can be obtained via a telemedicine or home / remote visit.

J 6 Data Capture During Telemedicine or Home / Remote Visits

Data collected during telemedicine or home/remote visits will be captured by the qualified HCP from the study site or TPV service in source documents, or by the participant themselves.

J 7 COVID-19 Vaccination

Investigators should follow their local prescribing information and policies when considering if vaccination against COVID-19 is appropriate for their patients participating in an AstraZeneca clinical trial.

Please consider the following if you are considering vaccinating your patient against COVID-19:

For a specific vaccine, consider the potential impact of its relevant prescribing information (ie, Indications, Contraindications, Warnings and Precautions, Adverse Reactions) on its use in the study population.

For patients with flexibility as to when to be enrolled in an AstraZeneca-sponsored study, vaccination prior to first dose of the trial investigational product(s) may be advisable.

Please contact the individual COVID-19 vaccine manufacturer if you have any questions concerning their product.

To better assess the overall impact of COVID-19 vaccination on a particular study and study population, ensure that both the COVID-19 vaccination details (including brand name and manufacturer) is captured in the eCRF as concomitant medication, and adverse reactions are reported.

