8.1.3.1.3 NRS-11 (adult cohort only)

The NRS-11 is a self-reported segmented 11-point numeric scale that assesses pain intensity (Hawker et al 2011). It consists of a horizontal line with 0 representing "no pain" at the left end of the line and 10 representing "worst pain you can imagine" at the right end. Subjects are asked to select the one number from 0 to 10 that best describes their worst pain over the past 7 days for the following: 1) physician selected target-tumour pain, 2) overall tumour pain, and 3) overall pain. It takes less than 1 minute to complete. The target tumour will be selected by the physician from a list of body locations in Table 9. The NRS-11 is recommended as a core outcome measure of pain intensity for clinical studies (Dworkin et al 2005; Wolters et al 2013). Adult subjects only will complete the NRS-11 for this study.

1	Head	16	Pelvic area
2	Еуе	17	Genitalia
3	Face	18	Upper arm
4	Ear	19	Forearm
5	Mouth/Tough	20	Hand
6	Neck (Front)	21	Thigh/Upper leg
7	Neck (Back)	22	Lower leg
8	Shoulder	23	Foot
9	Chest		
10	Armpit		
11	Flank		
12	Back (Upper)		
13	Back (Lower)		
14	Abdomen		
15	Buttock		

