9.4.4.1.3 NRS-11 (adult cohort)

The NRS-11 consists of 4 questions scored on an 11-point scale 0=no pain to 10=worst pain you can imagine. The primary outcome for the self-reported NRS-11 will be the rating of one specific tumour pain (e.g. the "target tumour"). This pain rating will be the physician-selected target tumour.

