9.5.4.1.3 NRS-11 (adult cohort)

Descriptive statistics for the pain intensity scores and change from baseline will be provided for each visit. A line graph with mean values/mean change from baseline values and

corresponding 95% CI will be presented. Other analyses may be performed as appropriate. Further details will be provided in the SAP.

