Appendix I Clinical outcome assessments

These PRO questionnaires are for information purposes and representation only and serve as an example of the questionnaire to be used in the study.

FLACC scale

Categories	Score 0	Score 1	Score 2		
Face	No particular expression or smile	Occasional grimace or frown, withdrawn, disinterested	Frequent to constant frown, clenched jaw, quivering chin		
Legs	Normal position or relaxed	Uneasy, restless, tense	Kicking, or legs drawn up		
Activity	Lying quietly, normal position, moves easily	Squirming, shifting back and forth, tense	Arched, rigid, or jerking		
Cry	No cry (awake or asleep)	Moans or whimpers, occasional complaint	Crying steadily, screams or sobs, frequent complaints		
Consolability	Content, relaxed	Reassured by occasional touching, hugging, or being talked to, distractable	Difficult to console or comfort		

FLACC Pain Assessment Tool

Pediatric Nursing 23(3), 293-297. © 2002, The Regents of the University of Michigan. All Rights Reserved.

E-code:

Assessment Date: _____ Enter FLACC Total Score:____

Assessment Time:

Initials of person administering the assessment:

Faces Pain Scale - Revised

Instructions

These faces show how much something can hurt. The face to the left shows no pain. The faces show more and more pain up to the right face - it shows very much pain. Please choose the face that shows the worst pain you had during the past week.

Source: Adapted from Hicks et al 2001.

Adult Pain Questionnaire

(Self-report form for adults)

Numeric Rating Scale - Pain Intensity

Below are some questions about how much you hurt. The first two questions are about how much your plexiform neurofibroma tumor or tumors hurt and the last question is about how much you hurt from all kinds of pain.

Below are lines with numbers from 0 to 10 where 0 means no pain and 10 means the worst pain you can imagine.

1. The doctor has picked the plexiform neurofibroma tumor in your body to measure for this study. We call this the "target tumor." We will ask you to tell us about that same tumor pain at each study visit.

Target tumor: _____

Please circle the one number that best describes the pain from your target tumor at its worst during the past 7 days.

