2. Do you have tumor pain in more than one place on your body? □ Yes □ No If yes, please circle the one number that best describes your overall tumor pain at its worst during the past 7 days.

3. Do you have other kinds of pain (for example, headaches or back pain)? \Box Yes \Box No

If yes, please circle the one number that best describes your overall pain at its worst during the past 7 days (including tumor pain and any other kinds of pain.)

Pain Interference Index

Self-report

Child/Adolescent Pain Questionnaires

(Self-report form for ages 8 – 18 years)

Pain Interference Index

Below you will find a list of questions about you and your pain. Please answer each question by circling one number between 0 and 6.

We are asking about your pain during the past 7 days.

In the past 7 days:

		Not at all			Some Completely			
1.	Has your pain made it hard for you to pay attention (for example, do classwork, homework, read)?	0	1	2	3	4	5	6
2.	Has your pain made it hard for you to do things outside of school (play/ free time activities)?	0	1	2	3	4	5	6
3.	Has your pain made it hard for you to spend time with friends?	0	1	2	3	4	5	6
4.	Has your pain affected your mood?	0	1	2	3	4	5	6
5.	Has your pain made it hard for you to do physical activities (like run, walk up stairs, play sports, do chores)?	0	1	2	3	4	5	6
6.	Has your pain made it hard for you to sleep?	0	1	2	3	4	5	6

Adapted by the Health Psychology and Neurobehavioral Research Group, NCI (10/28/15)

Parent report

Parent Pain Questionnaires

(Parent report form for children ages 5 - 18 years)

Pain Interference Index

Below you will find a list of questions about your child. Please answer each question by circling one number between 0 and 6.

We are asking about your child's pain during the past 7 days.

In the past 7 days:

		Not at all				Some		Completely
1.	Has your child's pain made it difficult for your child to pay attention (for example, do classwork, homework, read)?	0	1	2	3	4	5	6
2.	Has your child's pain made it difficult for your child to do things outside of school (play/free time activities)?	0	1	2	3	4	5	6
3.	Has your child's pain made it difficult for your child to spend time with friends?	0	1	2	3	4	5	6
4.	Has your child's pain affected your child's mood?	0	1	2	3	4	5	6
5.	Has your child's pain affected your child's ability to do physical activities (like run, walk up stairs, play sports, do chores)?	0	1	2	3	4	5	6

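### The Appendix I form asks for two supporting NRS-11 ratings only after a Yes, while Section 8.1.3.1.3 has every adult give all three

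*Protocol*

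**What the plan says.** Protocol Section 8.1.3.1.3 describes the adult NRS-11 without any condition: "Subjects are asked to select the one number from 0 to 10 that best describes their worst pain over the past 7 days", for "1) physician selected target-tumour pain, 2) overall tumour pain, and 3) overall pain".

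The adult form in Appendix I is built differently. Its scale has a usable zero: "Below are lines with numbers from 0 to 10 where 0 means no pain and 10 means the worst pain you can imagine". The first item, target-tumour pain, is put to everyone: "We will ask you to tell us about that same tumor pain at each study visit". The second item opens with "Do you have tumor pain in more than one place on your body", and the overall tumour pain rating is requested only after a Yes. The third opens with "Do you have other kinds of pain (for example, headaches or back pain", and the overall pain rating, which by the form's own wording includes tumour pain, is again requested only after a Yes. The form does not tell a subject who answers No to enter 0 or any other number.

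Section 9.4.4.1.3 states "The NRS-11 consists of 4 questions scored on an 11-point scale" and makes the physician-selected target tumour the primary NRS-11 outcome. Section 9.5.4.1.3 plans: "Descriptive statistics for the pain intensity scores and change from baseline will be provided for each visit", with line graphs of means and 95% confidence intervals. Section 9.5 leaves the handling of missing data to the SAP, which is not shown. Section 8.1.3 presents Appendix I as holding copies of the instruments used, whereas Appendix I labels its forms as examples.

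**The concern.** Whether a number exists for overall tumour pain or overall pain depends on the subject's pain at that visit. An adult with several painful sites at baseline who improves to one site, or to none, answers No and records nothing, although the scale has a zero. An adult who develops a second painful site, or a new kind of pain, has a score at follow-up and none at baseline. An adult with severe tumour pain and no other pain never records an overall pain score.

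A summary of recorded numbers would then describe a group that changes from visit to visit for reasons tied to the outcome. The two effects run in opposite directions: losing those who improve hides benefit, and losing those who newly worsen hides harm. At stake are two of the three NRS-11 scores that serve the secondary objective on pain in the adult cohort of about 16.

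**Working it through.** **Consistency of the text.**

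| Place | Ratings | Condition |
|---|---|---|
| Section 8.1.3.1.3 | 3 | none |
| Appendix I form | 3 | items 2 and 3 only after a Yes |
| Section 9.4.4.1.3 | 4 questions | none mentioned |

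The form has 3 ratings and 2 Yes/No gates, 3 + 2 = 5 questions in all. Neither 3 nor 5 gives the 4 in Section 9.4.4.1.3.

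**What a No means.**

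- Question 2, no tumour pain: the target item is 0, so overall tumour pain is 0 and can be derived.
- Question 2, tumour pain only at the target: overall tumour pain equals the target rating and can be derived.
- Question 2, tumour pain only at one non-target site: the target item is 0 but overall tumour pain is not. No number on the form supplies it.
- Question 3, no other kinds of pain: overall pain equals overall tumour pain, so it can be derived wherever that is known.

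A No is therefore not the same as 0, and setting every No to 0 would be wrong. Nor is every No recoverable.

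**Size if only recorded scores are used.** The protocol states no figure to reproduce. The only input taken from it is an adult cohort of about 16 (Section 9.2). The rest is assumed: all n = 16 have the gated score at baseline with value b, r of them become pain-free and answer No, and the others change by -1.

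Mean change in all 16 = [r × (-b) + (16 - r) × (-1)] / 16

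Mean change in those with a recorded score = -1

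Understatement = r × (b - 1) / 16

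- b = 5, r = 4: all 16 give (-20 - 12)/16 = -2.0; recorded only (n = 12) gives -1.0; understatement 1.0.
- Smallest case, b = 3, r = 2: 2 × 2/16 = 0.25.
- Largest case, b = 7, r = 8: 8 × 6/16 = 3.0.

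In this illustration every resolver has a target rating of 0, so deriving overall tumour pain from item 1 restores the full-cohort mean.

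**Size of what derivation cannot restore.** Suppose one adult has a target rating of 0 and pain x at a single non-target site. The derived score is 0, and the visit mean over 16 is too low by x/16. For x from 3 to 7 (the same assumed range), that is 3/16 = 0.19 to 7/16 = 0.44 points per such adult. The documents do not say how many such adults to expect.

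Newly worsening adults are not quantified. Their omission from the change summaries would shift the mean the opposite way.

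**The case against.** The strongest case against has four parts.

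First, the outcome that the protocol ranks first, target-tumour pain, has no gate. An adult whose target-tumour pain resolves records 0 and stays in the analysis. This stands. A reader might infer that adults whose pain resolves drop out of the NRS-11 analysis as a whole, or that the adult pain objective will be misreported. The documents do not support that. The PGIS also asks every adult about tumour pain and overall pain with no gate, and the PII and the QLQ-C30 pain scale cover pain as well. The PGIS does not replace the two scores, however: it is exploratory, uses six categories and asks about today.

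Second, most No answers are logical skips whose value follows from item 1. This also stands, and it limits the loss mainly to pain at a single non-target site.

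Third, the protocol nowhere says that No responders are excluded, and it assigns missing-data rules to the SAP. This stands in part. Exclusion is what results from using recorded numbers as they are; it is not a stated rule. But a SAP cannot recover a rating that was never asked for, and the contradiction lies within the protocol.

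Fourth, Appendix I calls its forms examples, and the tablet logic is not shown. That leaves open whether the gate is in use. It does not remove the need to reconcile, because Section 8.1.3 calls the same forms copies of what is used.

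**Conclusion.** The point holds for overall tumour pain and overall pain only. The form, Section 8.1.3.1.3 and Section 9.4.4.1.3 give three incompatible accounts of the instrument. If the form is used as printed and only recorded scores are summarised, missing values depend on pain itself: those who improve lose their follow-up score, and those who newly worsen lack a baseline. The 0.25 to 3.0 point range rests wholly on assumed baselines, assumed numbers resolving and an assumed change of -1 in the rest, and covers only the direction that hides benefit. It shows the mechanism and does not forecast this trial's result. Much of that loss can be undone by derivation from the target-tumour rating; pain at a single non-target site cannot be recovered. This should be corrected, but it does not threaten the primary NRS-11 outcome or the primary objectives.

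**What to change.** Reconcile the form with Section 8.1.3.1.3: program the tablet so that all three 0 to 10 ratings are mandatory for every adult at every visit, with 0 allowed. Correct the count in Section 9.4.4.1.3 to three ratings.

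For data already collected under the gate, or if the form cannot be changed, fix a scoring rule in advance. Score a No on question 2 as the target-tumour rating, and a No on question 3 as the higher available tumour rating. Flag every derived value, and state that the rule understates pain at a single non-target site.

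The cost is a tablet setting and one wording correction, or a short scoring rule. No visits or subjects are added.
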